2.2. BACKGROUND - CLINICAL STUDIES

2.2.1. Clinical Pharmacokinetics

At the time of study initiation, GLPG1205 or placebo had been administered to 98 healthy subjects in total in 4 Phase I clinical studies for which results have been reported. Additionally, 63 subjects with moderate to severe ulcerative colitis had been exposed to GLPG1205 100 mg q.d. or placebo for 12 weeks in one Phase II clinical study.

In healthy male subjects, GLPG1205 was rapidly absorbed with a median time to maximum plasma concentration of 2 to 4 hours. After q.d. oral dosing for 14 days, steady state in GLPG1205 plasma concentrations was reached by Day 10, with an overall accumulation ratio of 5.4 which is consistent with the long half-life of approximately 100 h. Steady-state exposure of GLPG1205 increased in proportion between 50 to 100 mg GLPG1205 q.d. Excretion of unchanged GLPG1205 in human urine was low (<0.5% in 24 h) and rapid.

Steady-state concentrations were reached by Day 2 instead of Day 10, if a 250-mg loading dose on Day 1 was followed by a 50-mg q.d. maintenance dose up to Day 14.

After 14-day q.d. administration of 50 mg as oral dose in 3 age groups of subjects (18 to 50 years, 65 to 74 years and 75 years or older); regardless of the age, steady state was attained within 9 dosing days and despite a trend for higher exposure in the age group 65 to 74 years, there was no statistical difference in PK parameters between the 3 age groups. Based on these data it could not be concluded that age has an impact on GLPG1205 bioavailability.

The between-subject variability in GLPG1205 PK after multiple doses was low for C_{max} and AUCs as shown by maximum coefficients of variation of around 30%.

After dosing with 100 mg GLPG1205 q.d. for 13 days, co-administration with a cocktail of sensitive substrates for CYP2C9 (warfarin), CYP2C19 (omeprazole) and CYP1A2 (caffeine) on the last dosing day indicated that GLPG1205 does not interact with these CYP enzymes in human.

The oral bioavailability of GLPG1205 given as 100 mg capsules was similar to that of 90 mg as aqueous nanosuspension used in the first-in-human study (in-between-studies comparison), and was not affected by food.

The PK of GLPG1205 in subjects with ulcerative colitis were similar to those observed in healthy subjects at the same dose levels.

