7. Safety blood sampling for clinical laboratory evaluations (hematology, coagulation and clinical chemistry)
8. [REDACTED]
9. [REDACTED]
10. Safety urine sampling for clinical laboratory evaluations (urinalysis)
11. Dosing IMP and if applicable nintedanib or pirfenidone on site
12. Postdose PK blood sample (± 2 hour postdose sample for GLPG1205, and if applicable nintedanib or pirfenidone concentration analyses)
13. Dispense subject diary and provide instructions on IMP intake, timing and storage
14. Collect subject diary
15. Dispense IMP
16. Collect returned IMP and review IMP compliance

Addendum for Visit 3 to Visit 8:

Alternative approach due to COVID-19 pandemic

If a study participant cannot conduct a study visit on site, the investigator will follow an alternative visit approach to ensure the safety of the subject and will conduct a remote visit (e.g., phone call, virtual visit) or home visit, to evaluate the safety of the patient, and to decide whether continuation in the study is justifiable.

The investigator should at least discuss the following items and collect the following information as much as possible:

- the subject's general condition
- information on any adverse events (changes of ongoing or new events)
- information on study medication intake
- information on standard of care medication intake
- information on concomitant medication intake
- completion of subject diary pages and Quality of Life Questionnaire by the study subject.

The investigator should consider local laboratory testing, physical examination, vital signs and ECG, whenever possible. These local data will not become part of the clinical database. These results should be stored as part of the source documentation at the clinical site to be available as necessary. In case any of the results are deemed clinically significant by the investigator, the corresponding AE needs to be reported in the eCRF.

Visit 9/EOT and Visit 10/EOS (if applicable)

Subjects who are taking nintedanib or pirfenidone can do this at home or on site according to their normal routine.

1. SGRQ (Visit 9/EOT)
2. Physical examination (including weight)
3. AE assessment and concomitant medication
4. 12-lead ECG (single)
5. Vital signs (supine SBP, DBP, heart rate, oral or tympanic body temperature, and respiratory rate)
6. Spirometry

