7.3.4.1. Primary Efficacy Endpoint Analysis

The change from baseline in FVC at 26 weeks will be analyzed using an analysis of covariance (ANCOVA) model including treatment, sex and stratum as categorical covariates

and age, height and baseline FVC value as continuous covariates. Subgroup analysis may be performed for background treatment.

As a sensitivity analysis, a random coefficient regression model (random slopes and intercepts) including treatment, sex and stratum as categorical fixed effects and time, age and height as continuous fixed effects, will be used to analyze the rate of decline in FVC. The treatment effect will be determined by using estimated slopes for each study group on the basis of the time-by-treatment interaction term from the mixed model. All available FVC values from baseline to Week 26 will be used including FVC measurements at the follow-up visit for subjects who discontinue the study medication prematurely and do not complete the study visits through Week 26.

Furthermore, sensitivity analyses including multiple imputation methods may be performed using all randomized subjects to assess the impact of missing data on the primary efficacy analysis.

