2.3. Study Design

This study is a randomized, double-blind, parallel group, placebo-controlled, multicenter, Phase 2 study.

Approximately 60 eligible subjects with a centrally confirmed IPF diagnosis are planned to be randomized in a 2:1 ratio to GLPG1205 100 mg q.d. taken as 2 capsules, or matching placebo once daily (q.d.) administered for 26 weeks on top of local standard of care (SOC). Standard of care is defined as receiving nintedanib, pirfenidone, or neither nintedanib nor pirfenidone.

Individual dose reductions of GLPG1205 will be allowed once in case of intolerance or toxicity at the discretion of the investigator. Subjects may have their dose of investigational medicinal product (IMP) reduced from 100 mg (2 capsules) q.d. to 50 mg (1 capsule) q.d. for the remainder of the study. Should the intolerance or toxicity continue, IMP may be discontinued, and the subject may be withdrawn from the study.

[figure not shown]
During the course of the study (post randomization) further adaptations of the treatment with nintedanib or pirfenidone due to e.g. intolerance or initiation of either nintedanib or pirfenidone is allowed based on the medical needs of the individual as judged by the investigator.

Enrolled subjects will come to the clinical study center at screening, Day 1 (baseline), Week 2, Week 4, Week 8, Week 12, Week 16, Week 20, Week 26, and, if applicable (i.e. for early IMP discontinuation), the end of treatment visit (EOT). In addition, a follow-up visit will be planned 4 weeks after the last administration of IMP (i.e. Week 30/EoS). The end of the study is reached when the last follow-up visit as planned according the Schedule of Activities (Section 2.5) of the last subject is performed.

Subjects who stop IMP early need to be encouraged to complete the EOT and follow-up visit for safety assessments and pulmonary function, but will not be obliged to do so.

To enhance the safety of the subjects and integrity of the study data, an IDMC will be implemented and clinical endpoint adjudication will be performed. Details are stipulated in the study protocol and the respective charters.

A schematic diagram of the clinical study design is provided below.

The subjects will be in the study for a duration of approximately 34 weeks: up to 4 weeks of screening, 26 weeks of treatment, and 4 weeks of follow-up.

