3.3.3. Analysis Windows

All assessments, including data collected on unscheduled visits, will be allocated to analysis windows based on the relative day of the assessment (see Section 3.3.1) and according to the algorithm in Table 2. TLFs will present the analysis windows.

Table 2 Analysis Windows for All Endpoints:

Time point label	Target day	Interval lower bound	Interval upper bound
Baseline	1	-INF	1
Week 2	15	2	22
Week 4	29	23	43
Week 8	57	44	71
Week 12	85	72	99
Week 16	113	100	127
Week 20	141	128	162
Week 26	183	163	197
Week 30	211	198	+INF

INF=infinity

Addendum: alternative approach due to COVID-19 pandemic

The Urgent Safety Measures (USMs dated 02-April-2020) described in CSP Amendment 2 allow to enlarge the visit window at the end of the treatment period (Visit 9, Week 26; from -28 days up to +56 days) including extension of study medication intake, i.e. up to a maximum of 56 days beyond 26 weeks of treatment. Hence, for patients having to extend treatment due to COVID-19, this could potentially result in end-of-treatment assessments being allocated to the FU/W30 analysis window and thus having missing data for the primary analysis time point W26. To assess the impact of this ‘missing’ data on the efficacy results, sensitivity analyses will be included in which these specific assessments are assigned to W26.

Definition of Baseline

For all endpoints, except ECG parameters and spirometry, baseline is defined as the last non-missing value before the first study drug administration. If multiple values qualify as last value, the mean of these values will be used in the analysis.

For spirometry endpoints, the mean of the analysis values (detailed in Section 5.2.2 for spirometry) before the first dose of study medication (including screening, baseline and unscheduled values as applicable) will be used to define the baseline value to reduce variability.

For electrocardiogram (ECG), the baseline is defined as the mean of the last recorded triplicate before the first study drug administration. If no triplicate is available before the first dose of study medication intake, the mean of the last duplicate ECG will be used, otherwise, the last ECG value will be considered as baseline.

Selection of Visits

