5.2.2.2.1. Linear Mixed Model

A random coefficient regression model including sex, and stratum as categorical fixed effects and age, and height as continuous fixed effects and a random intercept and slope will be used to analyze the yearly rate of decline in FVC. The treatment effect will be determined by using estimated slopes for each study group on the basis of the time-by-treatment interaction term from the mixed model. The model will be fit using the SAS Proc Mixed procedure, details are in Appendix II. The assumptions of the model will be investigated graphically.

This approach provides another estimate for the primary endpoint. In addition, this model implicitly takes into account missing data under the assumption of missing-at-random (MAR).

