APPENDIX II: ADDITIONAL DETAILS ON MIXED MODEL PRIMARY ANALYSIS

Linear Mixed Model

As a sensitivity analysis for the primary analysis, the rate of decline in FVC over 6 months will be analyzed using a random coefficient regression model including sex, and stratum as categorical fixed effects and age, and height as continuous fixed effects and a random intercept and slope. The treatment effect will be determined by using estimated slopes for each study group on the basis of the time-by-treatment interaction term from the mixed model. Only post-baseline FVC values at planned time points, as specified in Section 2.5 and 3.3.3, will be used. The model will be fit using the SAS Proc Mixed procedure, details are below. The assumptions of the model will be investigated graphically.

The statistical model can be written as follows:

$$Y_{ij} = (\alpha + a_i) + (\theta + (\beta_T \theta) * Trt_i + g_i) * t_{ij} + \beta_S * Sex_i + \beta_A * Age_i + \beta_H * Height_i + \beta_{SOC} * (Standard\ of\ care)_i + \varepsilon_{ij}$$

Where

- Y_{ij} is the FVC value for subject i at time t_{ij} ,
- α and θ are the fixed effects for the intercept and slope, respectively,
- a_i and g_i are random effects for the intercept and slope for subject i , with $\mathbf{b}_i = (a_i, g_i)$ assumed to be independent and identically normally distributed with mean 0 and unstructured variance-covariance matrix for all i ,
- $(\beta_T \theta)$ is the effect of GLPG1205 on the slope,
- $\beta_S, \beta_A, \beta_{SOC}$ and β_H are subject specific demographic coefficients for sex, age, stratification factor (SOC; 2 levels) and height at baseline,
- $Trt_i = 0$ for placebo and $Trt_i = 1$ for GLPG1205, $(Standard\ of\ care)_i = 0$ for neither and $(Standard\ of\ care)_i = 1$ for pirfenidone or nintedanib,
- ε_{ij} is the random error for subject i at time t_{ij} , assumed to be independent and identically normally distributed with mean 0 and variance σ_ε^2 for all i, j .

If this model fails to converge, other structures will be tested for the variance-covariance matrix for the error terms (e.g. heterogeneous Toeplitz). Depending on the structure used, the random slope and random intercept may need to be dropped from the model. The structure with the best fit, based on Akaike's information criterion, will then be used.

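### SAP Appendix II does not exclude completers' Week 30 follow-up FVC from the slope sensitivity model, contrary to the protocol's data rule

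*SAP*

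**What the plan says.** SAP Appendix II gives the data rule for the random coefficient model: "Only post-baseline FVC values at planned time points, as specified in Section 2.5 and 3.3.3, will be used". The SAP 2.5 schedule has spirometry at Visit 10/EOS, and Table 2 in SAP 3.3.3 gives that visit its own analysis window: "Week 30 211 198 +INF". On timing, SAP 2.3 says that "a follow-up visit will be planned 4 weeks after the last administration of IMP (i.e. Week 30/EoS").

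The visible text and the SAS code in Appendix II contain no Week 26 cut-off, no exclusion for completers and no rule tied to the last dose. SAP 5.2 removes only data collected after lung transplant.

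Protocol 7.3.4.1 sets a different rule for the same model. It takes values from baseline to Week 26 and adds "FVC measurements at the follow-up visit for subjects who discontinue the study medication prematurely" who also do not complete the visits through Week 26. The visible part of SAP 5.5, where changes from the protocol are listed, does not mention a change here. Parts of 5.5 are redacted.

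Appendix II describes the target as the decline over six months. SAP 5.2.2.2.1 calls the same quantity a yearly rate and says of the model: "This approach provides another estimate for the primary endpoint". That endpoint is the change over 26 weeks.

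**The concern.** A programmer who follows Appendix II would include the Week 30 FVC of subjects who completed treatment. The model fits one straight line per arm from a common intercept, so a value taken after washout is treated as a further point on the GLPG1205 line. As the last time point it carries a lot of weight in the slope. It also lies beyond the 26-week span that the model is meant to describe.

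The model is one of the prespecified checks on the observed-case ANCOVA and is meant to show sensitivity to missing data. If it disagreed with the ANCOVA because of post-treatment values, a reader could wrongly put the difference down to missing data.

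**Working it through.** **Inputs from the documents.** Protocol 7.1 gives 40 and 20 evaluable subjects, 10% dropout (36 and 18), an SD of 200 mL for the Week 26 change, and true effects of 50 and 80 mL in a 50:50 mix, so 0.5 × 50 + 0.5 × 80 = 65 mL. Protocol 2.2.1 describes GLPG1205 accumulation as "consistent with the long half-life of approximately 100 h".

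**The plan's own figure.** SE = 200 × √(1/36 + 1/18) = 57.7 mL. P(observed effect > 40 mL) = 1 − Φ((40 − 65)/57.7) = 66.7%, and P(> 20 mL) = 1 − Φ((20 − 65)/57.7) = 78.2%. Protocol 7.1 states 67% and 78%, so the inputs reproduce it.

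**Drug remaining at follow-up.** 28 days = 672 h = 6.72 half-lives, and 0.5^6.72 = 0.9%.

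**Expected slope difference.** For the Appendix II model, the generalised least squares expectation is E(β) = (Σ n X′V⁻¹X)⁻¹ Σ n X′V⁻¹μ, summed over arms, with V = ZGZ′ + σ²I. X holds an intercept, time and treatment × time. Visits are Weeks 4, 8, 12, 16, 20 and 26, with or without Week 30. The true effect is linear up to 65 mL at Week 26, that is 130 mL/year.

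Assumptions not in the documents: residual SD σ of 60, 100 or 130 mL; intercept SD of 400 or 700 mL; slope SD per 26 weeks = √(200² − 2σ²), so that the Week 26 change keeps its SD of 200 mL; no intercept–slope correlation; complete data, with every subject a completer.

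| Treatment effect at Week 30 | Slope difference, mL/year | Change |
|---|---|---|
| Week 30 not used | 130 | none |
| 75 mL (65 × 30/26, still diverging) | 130 | none |
| 65 mL (kept, no longer growing) | about 117 | about −10% |
| 32.5 mL (half lost) | about 75 | about −42% |
| 0 mL (all lost) | about 33 | about −75% |

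For σ = 100 and intercept SD 400, the SE is 103.7 mL/year with Week 30 and 115.6 without, a rise of 115.6/103.7 − 1 = 11%. Over all the assumed values the rise is about 4–22%. In the −10% case the bias is 130 − 117 = 13 mL/year, and 13/115.6 = 0.11 SE.

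Restoring baseline FVC to the model, which the protocol includes and Appendix II omits, does not remove the effect: the three losses become about 8%, 34% and 60%.

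**The case against.** **Inclusion is inferred, not stated.** Appendix II speaks of six months, the 2.5 schedule places Visit 10 under follow-up, the SAP is based on the protocol that has the right rule, technical derivations sit in a separate document, and part of 5.5 is redacted. This stands to the extent that the text fails to exclude Week 30 rather than calling for it by name. It does not restore the limit: the six-month phrase describes the rate, not the data.

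**The bias is not established.** A reader might infer that Week 30 values necessarily pull the treatment difference toward zero. The documents give no FVC data after withdrawal. The half-life shows that drug leaves, not that preserved lung function is lost. The protocol presents IPF as irreversible and the benefit as less decline, which fits at most a gap that stops growing. In that case, keeping Week 30 gives the smaller root mean squared error: √(13² + 103.7²) = 104.5 against 115.6 mL/year in the example. This objection stands.

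**Off-drug values are not an error in themselves.** A reader might see this as contamination of an on-treatment analysis. The SAP does not call it one: efficacy uses the FAS, and the protocol's own rule takes off-drug follow-up values from early discontinuers. This stands. The valid objection is the time span and the departure from the protocol.

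**Week 30 is not off-drug for every subject.** An early discontinuer's follow-up visit can fall in an earlier window, and a Visit 9 delayed for COVID-19 can fall in the Week 30 window while the subject is still on treatment. This also stands, and it shapes the fix.

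**A large break would be visible.** Appendix II checks linearity with plots of observed FVC and LS means by time point. That helps interpretation but does not settle which data enter the model.

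**Conclusion.** The discrepancy is real and should be corrected. As written, Appendix II does not exclude completers' Week 30 FVC from the slope model, while protocol 7.3.4.1 does, and the visible SAP text does not declare the change.

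Its numerical effect depends on what happens to FVC after the last dose. If the benefit is kept but stops growing, the treatment-by-time difference falls by about 10%, or 13 mL/year, about 0.1 SE. The −42% and −75% figures are illustrations only; nothing in the documents supports a loss of half or all of the benefit within four weeks. If the arms keep diverging at the same rate, there is no bias. What shrinks is the difference between arms; the GLPG1205 arm's own decline would become steeper.

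A reader might infer that the primary result is at risk. It is not: the ANCOVA is fitted at each time point, and the MMRM gives each time point its own treatment effect, so neither Week 26 contrast averages in Week 30. The point concerns one sensitivity analysis. The sizes rest on the protocol's planning values and on the assumed variance components listed above.

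**What to change.** Replace the data rule for the slope model in Appendix II with the protocol's follow-up rule:

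- For subjects who complete treatment, use FVC up to and including Visit 9. Identify it by visit and last-dose date, not by the Week 30 window.
- Use Visit 10 FVC only for subjects who stop IMP early and do not complete visits through Week 26.

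Dropping the Week 30 window outright would be wrong, because it would discard on-treatment Visit 9 values delayed for COVID-19. The reassignment in SAP 5.2.2.2.4 does not rescue them here, since it covers only descriptive statistics, summary plots and the ANCOVA.

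If the sponsor prefers to keep Week 30 for completers, SAP 5.5 should declare the departure from protocol 7.3.4.1 and justify it, including the assumption about FVC after the last dose. The MMRM needs no change on this point.

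The work is a short text change and one data filter. The statistical cost is a slope SE about 4–22% larger under the stated assumptions, or about 2–18% if baseline FVC is also in the model.

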2.3. CLINICAL STUDY RATIONALE

IPF is a chronic and progressive lethal lung disease for which two oral treatments (pirfenidone and nintedanib) are approved in the EU and US. These treatments appear to slow disease progression however, the residual decline of FVC over one year remains substantial, with a further decline of FVC over 52 weeks of 125 mL and 114 mL in INPULSIS I and II (nintedanib) [16], respectively, and around 200 mL in the ASCEND study (pirfenidone) [15].

In addition, both compounds are frequently associated with side effects potentially limiting the use in clinical practice.

There thus remains a significant unmet medical need for the development of additional therapies targeting different disease pathways that could potentially prove to be more effective by further preventing the decline in FVC with an acceptable safety profile [22].

Recent published data suggest the relevance of GPR84 in fibrotic pathways underlined by GPR84 knock out mice used in models of kidney fibrosis [20]. In addition, PBI-4050 a compound in clinical development targeting both GPR84 and GPR40, has demonstrated first clinical benefit after 12 weeks of treatment in patients with IPF with and without addition of nintedanib [21]. It thus can be anticipated that compounds targeting GPR84 could lead to a new class of therapy for IPF.

GLPG1205 is a novel, selective, and potent GPR84 antagonist that has a good safety and tolerability profile at the targeted dose of 100 mg q.d. in clinical studies.

Consequently, it seems appropriate to investigate the efficacy, safety, tolerability and PK of GLPG1205 in subjects with IPF.

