Subjects are not allowed to use non-evidenced based medication being used to treat IPF (i.e. warfarin; imatinib; endothelin inhibitors such as ambrisentan, bosentan, and macitentan; azathioprine; cyclophosphamide; cyclosporine A; methotrexate; sildenafil; prednisone at steady dose >10 mg/day or equivalent glucocorticoid dose) within 4 weeks before screening and during screening, or planned during the study. Subjects are also not allowed to use any other experimental oral IPF therapy within 12 weeks or 5-half-lives of the agent, whichever is longer, prior to screening, or to have participated in an investigational drug antibody / biologic study within 6 months prior to screening. This is necessary in order to avoid any confounding effects these drugs may have on the safety, tolerability, PK, [REDACTED] endpoints evaluated in the current study.

According to the analysis of the course of disease in placebo treated IPF subjects in clinical studies over 12 months by Nathan et al. [23] approximately 9.5% IPF subjects may experience a $\geq 10\%$ decline in % predicted FVC after 6 months compared with baseline. Nintedanib and pirfenidone have been shown to have a beneficial effect on the rate of decline in lung function. It is anticipated that a potential efficacious effect of GLPG1205 in IPF can be substantiated after this period of time and distinguished from individual courses of the disease in both populations – patients receiving nintedanib, pirfenidone, or neither nintedanib nor pirfenidone.

Pirfenidone is primarily metabolized in humans via CYP1A2 with minor contributions from other CYP isoenzymes. A clinical study assessing the effect of GLPG1205 on a CYP1A2 probe substrate (caffeine) demonstrated that there was no impact of GLPG1205 on the CYP1A2 probe substrate (no inhibition nor induction).

Pirfenidone is a weak P-glycoprotein (P-gp) inhibitor and is a weak CYP2C9, 2C19 or 1A2, 2D6, and 3A4 inhibitor. GLPG1205 is not an efflux substrate (P-gp, BCRP, multidrug resistance-associated protein 2 [MRP2]) and has multiple CYPs involved in its metabolism (3A4, 2C19). Consequently, the coadministration of GLPG1205 with pirfenidone should not lead to drug interactions however plasma levels of both GLPG1205 and pirfenidone will be measured and tolerability will be closely monitored.

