4.4. MEASURES TO MINIMIZE BIAS

4.4.1. Randomization

At screening, subjects will be assigned a subject identification number using a centralized electronic system (interactive web response system [IWRS]). When subjects are confirmed to be eligible for the clinical study, the subject will be randomized in a 2:1 ratio to GLPG1205 or placebo. Allocation of each subject to a given treatment will be done via IWRS and will be stratified for background standard of care (subjects receiving nintedanib, pirfenidone, or neither nintedanib nor pirfenidone).

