3.4.4. Stratification Factors

The analyses will be stratified by the type of IPF SOC medication taken at randomization: nintedanib or pirfenidone or neither. In all analyses, except if indicated otherwise, the stratum will be the SOC at randomization and will not change if the subject switches SOC during the study.

The 3 strata could differ in their safety profile, in addition, they might have different effects on the biomarker results (depending on the biomarker) and efficacy results. Therefore, for all analyses, 3 strata will be used (nintedanib, pirfenidone, neither), unless indicated otherwise.

The stratum reported in the case report form (CRF) will be used in the analyses. Any discrepancies in stratification reported in the interactive web response system (IWRS) versus CRF will be listed.

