The linearity assumption of the model will be explored graphically by the line plots over time of the observed FVC values (mL) as well as change from baseline and LS means at each time point.

The following SAS code is to be used:

```
proc SORT data = FVC;
  BY subject visit;
run;
proc MIXED data = FVC order = internal;
  CLASS subject treatment visit sex stratum;
  MODEL FVC = treatment * time sex age height stratum / solution CL ddfm=KR;
  RANDOM intercept time / type=UN subject = subject;
  REPEATED visit / type= Simple subject = subject;
  ESTIMATE 'GLPG1205 – Placebo' treatment*time -1 1 / e CL;
run;
```

Repeated Measures Analysis

As a sensitivity analysis for the primary analysis, the change from baseline in FVC over 26 weeks will also be compared between treatment groups by MMRM including sex, stratum, and a treatment-by-time point interaction as categorical fixed effects, age, height, and baseline FVC as continuous fixed effects and correlated within-subject residuals. Only post-baseline FVC values at planned time points, as specified in Section 2.5 and 3.3.3, will be used. The model will be fit using the SAS Proc Mixed procedure, details are below.

The statistical model can be written as follows:

$$Y_{ij} = \alpha + (\theta_j + (\beta_T \theta)_j * Trt_i) + \beta_S * Sex_i + \beta_A * Age_i + \beta_H * Height_i + \beta_{SOC} * (Standard\ of\ care)_i + \beta_B * Baseline_i + \epsilon_{ij}$$

Where

- Y_{ij} is the FVC change from baseline for subject i at time point j (excluding baseline),
- α is the intercept and θ_j is the placebo time effect at time point j ,
- $(\beta_T \theta)_j$ is the effect of GLPG1205 at time point j ,
- β_S , β_A , β_{SOC} and β_H are subject specific demographic coefficients for sex, age, stratification factor (SOC; 2 levels) and height at baseline,

■ [REDACTED]

■ [REDACTED]

■ [REDACTED]

■ [REDACTED]

[REDACTED]

[REDACTED]

[REDACTED]

[REDACTED]

[REDACTED]

[REDACTED]

[REDACTED]

[REDACTED]

[REDACTED]

■ [REDACTED]

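### The random-slope FVC sensitivity model adjusts FVC level, but not rate of decline, for background antifibrotic; a stratum-by-time term is a small and nearly free improvement

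*SAP*

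**What the plan says.** The random-coefficient model is a sensitivity analysis of the primary endpoint (SAP 5.2.2.2.1 and Appendix II). Its target is a slope difference: "The treatment effect will be determined by using estimated slopes for each study group on the basis of the time-by-treatment interaction term". The SAS statement is "MODEL FVC = treatment * time sex age height stratum / solution CL ddfm=KR".

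In the Appendix II equation, only three things multiply time: the common slope, the treatment effect on the slope, and the subject's random slope. Standard of care stands outside that bracket, among the "subject specific demographic coefficients for sex, age, stratification factor (SOC; 2 levels) and height at baseline". Protocol 7.3.4.1 describes the same structure, "including treatment, sex and stratum as categorical fixed effects and time, age and height as continuous fixed effects", with no stratum-by-time term.

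Randomisation is "stratified for background standard of care (subjects receiving nintedanib, pirfenidone, or neither nintedanib nor pirfenidone" (Protocol 4.4.1), which is three levels. SAP 3.4.4 says that "The analyses will be stratified by the type of IPF SOC medication taken at randomization", with three strata unless indicated otherwise. Protocol 2.3.2 states: "Nintedanib and pirfenidone have been shown to have a beneficial effect on the rate of decline in lung function". Protocol 2.3 cites "a further decline of FVC over 52 weeks of 125 mL and 114 mL" on nintedanib and around 200 mL on pirfenidone. Neither document gives a rate of decline for patients on neither drug.

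**The concern.** A main effect of background removes differences between groups in FVC level. For a slope contrast these matter little, because the random intercept already absorbs them. Differences between groups in slope stay in the random-slope variance.

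Stratified randomisation balances those differences across arms, so they add almost nothing to the real error of the treatment contrast. The model does not know this and counts them in the standard error.

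The primary ANCOVA (SAP 5.2.2.1) models the change itself with stratum as a covariate, so it does adjust the change for background. The slope analysis therefore departs from the analysis it is meant to check for a reason unrelated to missing data. The model is offered partly because it handles data missing at random, so it also matters whether dropout related to background could move its estimate.

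**Working it through.** **1. The plan's own figures.** Protocol 7.1 assumes an SD of 200 mL for the Week 26 change, effects of 50 mL (on antifibrotic) and 80 mL (on neither), a 50:50 split, 40 and 20 subjects, and 10% dropout (36 and 18).

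- Mean effect = 0.5×50 + 0.5×80 = 65 mL.
- SE = 200×√(1/36 + 1/18) = 57.74 mL.
- P(observed > 40) = Φ(25/57.74) = 66.75%; P(observed > 20) = Φ(45/57.74) = 78.2%.

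These reproduce the stated 67% and 78%. No SE or power is stated for the slope model.

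**2. Effect of leaving out stratum*time.** Let D be the difference in 26-week decline between two background groups and p the share in one of them. Omitting the term adds p(1−p)D² to the variance of the 26-week change, so

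SE ratio = √(1 + p(1−p)D²/200²).

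The documented gap: nintedanib (125+114)/2 = 119.5 mL per 52 weeks, about 60 per 26; pirfenidone about 200/2 = 100. So D is about 40 mL, across different trials. As p(1−p) is at most 0.25, the ratio is at most √(1 + 0.25×1600/40000) = √1.01, an excess of about 0.5%. The other values of D are assumptions, taken at p = 0.5.

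| D (mL per 26 weeks) | SE with term | SE without | Excess, formula | Excess, simulation |
|---|---|---|---|---|
| 0 | 57.74 | 57.74 | 0% | 0.1% |
| 40 | 57.74 | 58.02 | 0.5% | not run |
| 50 | 57.74 | 58.18 | 0.8% | 0.3% |
| 100 | 57.74 | 59.51 | 3.1% | 2.1% |
| 150 | 57.74 | 61.66 | 6.8% | 5.3% |

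At p = 0.8 the formula gives 2.0% (D = 100) and 4.4% (D = 150). Approximate power for 65 mL is 20.2% with the term. Without it, power is 20.0%, 19.3% and 18.3% at D = 50, 100 and 150.

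**3. Simulation.** 1,000 trials per D, 36:18, randomisation stratified on two background groups, visits at Weeks 4 to 26, REML. Assumed residual SD 80 mL and intercept SD 600 mL; slope SD √(200² − 2×80²) = 165 mL, so that the change has SD 200.

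The simulated excess is lower than the formula because the group on neither drug was given the larger effect. That narrows the gap averaged over arms by (2/3)×30 = 20 mL. Putting D − 20 into the formula gives 0.3%, 2.0% and 5.1% at D = 50, 100 and 150, in line with the simulation.

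The mean estimate was 69.4 mL with and without the term. This lies above 65 by about 2.4 Monte Carlo errors of 1.9 mL, but the comparison is paired on the same simulated trials. The true sampling SD was 58.6 to 58.7 mL throughout. The mean SE of the planned model was 57.4, 57.5, 58.5 and 60.3 at D = 0, 50, 100 and 150, so it exceeded the true SD only at 150.

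**4. Unequal dropout.** Expected generalised least squares estimates were computed for 40:20 subjects, equal strata, a true effect of 65 mL, slope SD 120, residual SD 100 and intercept SD 600. Declines were 60 and 100 mL (nintedanib, pirfenidone) and an assumed 100, 150 or 200 mL on neither. Dropout was after Week 8.

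- 10% everywhere: 65.0 mL, no bias.
- 40% on GLPG1205 plus nintedanib, 10% elsewhere (both assumed): about 62, 60 and 58 mL as written; 65.0 with stratum*time on three levels.

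**The case against.** The case for leaving the model alone is substantial, and most of it stands.

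- **The excess is conditional.** It exists only if background groups decline at different rates, and no rate is given for patients on neither drug. Protocol 2.3.2 says about 9.5% of placebo patients lose 10% or more in % predicted FVC by 6 months. Read as percentage points, with normality and SD 200 mL, the mean decline is 10% of predicted FVC minus 1.31×200 = 262 mL. For an assumed predicted FVC of 3.0–4.0 L that is about 40–140 mL. Against about 60 mL on nintedanib, the gap is then at most about 80 mL, or 2.0% (√1.04). The 100 and 150 mL rows are therefore generous.
- **Trial features may narrow the gap.** All subjects must show FVC decline in the prior 9 months (inclusion criterion 5.1), and those on neither drug may start one during the study. The calculations model neither feature.
- **Background is handled elsewhere.** The primary ANCOVA and the MMRM model change from baseline with stratum as a covariate, and SAP 5.2.5 adds estimates by stratum. The slope model is meant to give another estimate, in a non-confirmatory study.

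A reader might also infer that the SAP breaks its own rule in 3.4.4. The documents do not support that. The section does not ask for a stratum-by-time term, the SAP's other models also implement stratification as a covariate, and Protocol 7.3.4.1 prespecifies the same main effect.

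What does not fall away is that, for a slope, a level-only term is not an adjustment of the thing estimated. The protocol itself says background therapy acts on that thing.

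**Conclusion.** The point holds as a minor one. The treatment-by-time contrast in Appendix II is not adjusted for background antifibrotic. If background groups decline at different rates, its reported SE is conservative by about 0.5% for the documented 40 mL gap, about 2–3% for an assumed 100 mL gap and about 5–7% for an assumed 150 mL gap. With balanced dropout the estimate is unbiased. With dropout that depends on both stratum and arm it can shift by a few mL (3 to 7 mL in the assumed 40% scenario; that rate is not in the documents).

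Two stronger readings should be avoided. The SE cannot be called too wide without condition: at gaps of 0 and 50 mL it was not above the true sampling SD. Nor does the plan throw away subjects. Translating a 5% SE excess into 1.05² ≈ 1.10, or about 6 of 60 subjects, needs a decline on neither drug that the documents do not give. It also mistakes a conservative reported SE for a less precise estimator, when the true sampling SD barely changes. The primary analysis is not touched.

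**What to change.** Add a standard-of-care-by-time term inside the time bracket of the Appendix II equation, and change the code to `MODEL FVC = treatment*time stratum stratum*time sex age height` with the same options. Keep the treatment*time ESTIMATE as it is; it then gives the slope difference adjusted for background slope.

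Use the three randomised strata if possible. Appendix II pools nintedanib and pirfenidone into one level, so a two-level interaction could not remove the one gap the protocol documents.

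The interaction costs one parameter with two levels or two with three; taking the main effect from two to three levels as well adds one more. SAP 5.2.2.2 already allows sensitivity analyses to be added before unblinding for the final analysis, so the change should be specified by then. Protocol 7.3.4.1 has the main effect only, so record the added term in SAP 5.5.
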